**Secondary objectives:****Humoral immunogenicity after third dose**

The intent of this secondary objective is to evaluate the improvement of the persistence of antibody response at one month after a third injection. An increase in the antibody titres compared to the second dose is expected.

Approximately a 10% drop out is expected for the third dose evaluation (given at 6 months for one arm and at 12 months for the other arm) and thus 90 evaluable subjects are expected to be analysed for the humoral immunogenicity evaluation.

A sample size of 90 evaluable subjects achieves 90% power to detect a difference of 0.256 between the null hypothesis mean of 0.0 and the alternative hypothesis mean with a known standard deviation of 0.83 and with a significance level (alpha) of 0.05 using a one-sided one-sample t-test.

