| Eligible:                                  | 
Qualified for enrolment into the study based upon strict adherence to inclusion/exclusion criteria.
  |
| End of Study
(Synonym of End of Trial) | 
For studies without collection of human biologicals samples or imaging data EoS is the Last Subject Last Visit (LSLV).
 
For studies with collection of Human Biologicals Samples or imaging data, EoS is defined as the date of the last testing/reading released of the Human Biological Samples or imaging data, related to primary and secondary endpoints. EoS must be achieved no later than 8 months after LSLV.
   |
| Epoch:                                     | 
An epoch is a set of consecutive timepoints or a single timepoint from a single protocol. Epochs are defined to support a main purpose which is either to draw conclusions on subject participation or to draw a complete conclusion to define or precise the targeted label of the product. Supporting means that data
  |

**CONFIDENTIAL**207759 (NTHI MCAT-008)  
Protocol Amendment 3 Final

collected at the timepoints included in an epoch must be sufficient to fulfil the purpose of the epoch.

Typical examples of epochs are screening, primary vaccinations, boosters, yearly immunogenicity follow-ups, and surveillance periods for efficacy or safety.

|  |   |
|--|---|
| eTrack:   | GSK's tracking tool for clinical trials.  |
| Evaluable:  | Meeting all eligibility criteria, complying with the procedures defined in the protocol, and, therefore, included in the per-protocol analysis (see Sections 6.6.2 and 10.5 for details on criteria for evaluability).  |
| Former smoker:  | A person who stopped smoking for at least 6 months at the time of study start.  |
| Immunological correlate of protection:  | The defined immune response above which there is a high likelihood of protection in the absence of any host factors that might increase susceptibility to the infectious agent.   |
| Investigational vaccine:
(Synonym of Investigational Medicinal Product) | A pharmaceutical form of an active ingredient being tested in a clinical trial, including a product with a marketing authorisation when used in a way different from the approved form, or when used for an unapproved indication, or when used to gain further information about an approved use.  |

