**10.4. Determination of sample size****Primary objective**

In this study, a third injection will be given either at 6 months or at 12 months in order to verify the safety of the third dose.

**CONFIDENTIAL**207759 (NTHI MCAT-008)  
Protocol Amendment 3 Final

Considering the sample size of 100 in each vaccination schedule, [Table 19](#) illustrates the precision we can get on the percentage of subjects with grade 3 symptoms following a third vaccination.

A sample size of 100 subjects allows a 2-sided 95% confidence interval with a width equal to 0.165 when the sample proportion is equal to 20%, using a simple asymptotic formula.

**Table 19** Exact confidence interval for one proportion

| % of subjects with a symptom | N=100 subjects                     |             | N=90 subjects*                     |             |
|------------------------------|------------------------------------|-------------|------------------------------------|-------------|
|                              | Exact 95% Confidence Interval (CI) |             | Exact 95% Confidence Interval (CI) |             |
|                              | Lower Limit                        | Upper limit | Lower Limit                        | Upper limit |
| 0                            | 0.0                                | 3.6         | 0.0                                | 4.0         |
| 5                            | 1.6                                | 11.3        | 1.5                                | 11.7        |
| 10                           | 4.9                                | 17.6        | 4.7                                | 18.1        |
| 15                           | 8.6                                | 23.5        | 8.3                                | 24.1        |
| 20                           | 12.7                               | 29.2        | 12.3                               | 29.8        |
| 25                           | 16.9                               | 34.7        | 16.5                               | 35.2        |
| 30                           | 21.2                               | 40.0        | 20.8                               | 40.6        |
| 35                           | 25.7                               | 45.2        | 25.2                               | 45.8        |
| 40                           | 30.3                               | 50.3        | 29.8                               | 50.9        |

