## **10.9. Analysis of immunogenicity**

The analysis will be performed on the PPS at first line. If the percentage of vaccinated subjects with serological results excluded from the PPS is more than 10%, a second analysis will be performed on the FAS.

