**11.2.4. Immunogenicity**

- For a given subject and given immunogenicity measurement, missing or non-evaluatable measurements will not be replaced. Therefore, an analysis will exclude subjects with missing or non-evaluatable measurements.
- The Geometric Mean Concentrations (GMC) calculations are performed by taking the anti-log of the mean of the log concentration transformations. Antibody concentration below the cut-off of the assay will be given an arbitrary value of half the cut-off of the assay for the purpose of GMC calculation. Antibody concentration above the assay cut-off (i.e. the ELISA upper limit of quantification) will be given twice the cut-off value.
- A seronegative subject is a subject whose antibody concentration is below the cut-off value of the assay. A seropositive subject is a subject whose antibody concentration is greater than or equal to the cut-off value of the assay.
- All CIs computed will be two-sided 95% CIs.

**CONFIDENTIAL**207759 (NTHI MCAT-008)  
Statistical Analysis Plan Amendment 1 Final**11.2.5. Safety**

Solicited adverse event: with the exception of 60 minutes after vaccination, solicited adverse events are collected via paper-diary and thus no DCF (data clarification form) will apply in case of inconsistency reporting.

For a given subject and the analysis of solicited symptoms within 7 days post-vaccination, missing or non-evaluable measurements will not be replaced. Therefore the analysis of the solicited symptoms based on the Solicited Safety Set will include only vaccinated subjects for doses with documented safety data (i.e., symptom screen completed). More specifically the following rules will be used:

- subjects who documented the absence of a solicited symptom after one dose will be considered not having that symptom after that dose;
- subjects who reported solicited safety data at a visit, but they didn't report any daily measurement for a certain symptom, they will be counted as missing for that symptom at that visit;
- subjects who documented the presence of a solicited symptom and fully or partially recorded daily measurement over the solicited period will be included in the summaries at that dose and classified according to their maximum observed daily recording over the solicited period;
- doses without symptom sheets documented will be excluded;

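### The 90% power quoted for the third-dose antibody rise belongs to a one-sided 5% test that is not in the analysis plan; for the planned two-sided 95% interval it is about 82–83% with 90 subjects, before any per-protocol exclusions

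*Protocol*

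**What the plan says.** **Sample size.** Protocol 10.4 starts from 100 subjects per schedule. For the humoral objective it states: "Approximately a 10% drop out is expected for the third dose evaluation", and concludes that "thus 90 evaluable subjects are expected to be analysed for the humoral immunogenicity evaluation". It then states: "A sample size of 90 evaluable subjects achieves 90% power to detect a difference of 0.256 between the null hypothesis mean of 0.0". The inputs are a null mean of zero, an SD of 0.83 described as known, alpha 0.05 and a one-sided one-sample t-test. The paragraph expects titres to rise relative to the second dose. It does not name the two timepoints being compared or the scale of 0.256 and 0.83.

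**Analysis.** Protocol 10.9.1 and SAP 6.4.1.1.1 plan GMCs, seropositivity rates and fold-increase percentages with 95% intervals. The SAP adds geometric mean ratios (GMRs) against Day 1, Day 181 and Day 361. SAP 11.2.4 fixes the level: "All CIs computed will be two-sided 95% CIs". Protocol 10.10 describes the purpose as estimation, plans no comparisons, and sets a 5% alpha for any that are made.

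**Population.** Protocol 10.9 says: "The analysis will be performed on the PPS at first line". The protocol glossary describes an evaluable subject as meeting eligibility, "complying with the procedures defined in the protocol, and, therefore, included in the per-protocol analysis".

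**The concern.** Two things in the power statement do not match the rest of the plan.

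First, the powered test and the planned output use different error levels. Someone judging from the reported interval whether the third dose raised titres will look at whether its lower limit is above no change. For a two-sided 95% interval that is a one-sided 2.5% criterion, half the alpha used in 10.4.

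Second, 10.4 reaches 90 evaluable subjects by removing drop-outs alone. Under the glossary, evaluable means included in the per-protocol set (PPS). That set also excludes subjects for eligibility violations, forbidden medication or vaccines, intercurrent conditions, and missed vaccination or sampling windows (Protocol 10.5.3 and Table 6; SAP 5.2.3.1). Nothing is allowed for these.

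At stake is how a non-conclusive result is read. If an interval includes no change, a reader relying on 10.4 will put the chance of missing a true rise of 0.256 at 10%. For the interval actually reported it is nearer 17%, and higher if the PPS is smaller than 90.

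**Working it through.** **Inputs** (all from Protocol 10.4): n = 90, difference d = 0.256, SD s = 0.83, one-sided alpha 0.05. The two-sided 95% level is from SAP 11.2.4. PPS losses beyond drop-out are assumed, because the documents give no rate.

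**Formulas.** Noncentrality: λ = d·√n / s. Known SD: power = Φ(λ − z). Unknown SD: power = P(T > t), where T is noncentral t with n − 1 degrees of freedom and noncentrality λ, and t is the central-t critical value. For the two-sided interval the critical value is the 97.5% point. The chance of an interval wholly below no change is negligible here.

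**Step 1: reproduce the plan's figure.** λ = 0.256 × √90 / 0.83 = 2.926.
- Known SD: Φ(2.926 − 1.645) = Φ(1.281) = 90.0%.
- t, 89 df, critical value 1.662: 89.6%.

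The stated 90% reproduces. It is exactly the known-SD figure; the named t-test gives 0.4 points less, which rounding removes.

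**Step 2: same inputs, two-sided 95% interval.**
- Known SD: Φ(2.926 − 1.960) = Φ(0.966) = 83.3%.
- t, 89 df, critical value 1.987: 82.5%.

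The chance of missing the rise is therefore 16.7% or 17.5%, against the 10% implied.

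**Step 3: difference giving a 90% chance at n = 90, two-sided 95%.**
- Known SD: (1.960 + 1.282) × 0.83 / √90 = 0.284.
- t, solved numerically: 0.287.

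**Step 4: smaller PPS (assumed further loss from 90), two-sided 95%.**

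| Further loss | n | λ | Known SD | t |
|---|---|---|---|---|
| none | 90 | 2.926 | 83.3% | 82.5% |
| about 5% | 85 | 2.844 | 81.2% | 80.3% |
| 10% | 81 | 2.776 | 79.3% | 78.3% |
| 20% | 72 | 2.617 | 74.4% | 73.3% |

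**Limits of the calculation.** The SAP obtains GMRs from a model fitted to both groups with country, age category and smoking status (SAP 6.4.2.1), so one-sample figures are approximations. They are per antigen and per schedule. They also take 0.256 and 0.83 to describe a within-subject change, which 10.4 implies but does not say.

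**The case against.** **The 90% is correct and its basis is disclosed.** Protocol 10.4 states the alpha, the sidedness and the known SD. This stands. A reader might infer an arithmetic slip; there is none, and the z-versus-t difference is immaterial.

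**No success rule exists.** Neither document says that an increase is shown when the lower limit passes no change. Protocol 10.10 and SAP section 7 describe estimation, and a two-sided interval is a reporting convention. This also stands: 82–83% is not the power of a planned test. It is the chance that the planned interval lies wholly above no change. That is still the closest counterpart of the 10.4 statement in what the study will report, and the one-sided test has no counterpart there.

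**The PPS loss is speculative.** The 10% in Protocol 10.9 is a trigger for a second analysis on the full analysis set, not a forecast, and the approximate 10% in 10.4 might be a round allowance for every kind of loss. It is right that no particular rate can be assumed. A reader might take 78% as the plan's true power; the documents do not support that, so the losses appear only as a range. The wording problem remains, because 10.4 calls its allowance drop-out and then calls the remainder evaluable.

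**The contrast is undefined.** 10.4 refers to the second dose, but the SAP plans no GMR against Day 91, the post-second-dose sample. This stands, and is a further reason to name the contrast when the paragraph is restated.

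**Conclusion.** The concern holds as a mismatch between the power statement and the planned output. For 90 subjects, a difference of 0.256 and SD 0.83, the figure matching the planned two-sided 95% interval is about 83% (known SD) or 82% (t), roughly 7 points below the stated 90%. This does not depend on any assumption about the PPS. It does rest on the protocol's own difference and SD and on the one-sample approximation. Any reduction below 82–83% rests on an assumed exclusion rate.

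Two further readings go too far. A reader might conclude that the trial is too small; but the primary safety objective is sized on interval precision and event probability and is unaffected, and the humoral objective is secondary and estimation-based. A reader might also extend the figures to a chance of success across all four antigens; no joint criterion is planned and no joint power follows from the inputs given. Severity is minor.

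**What to change.** Restate the humoral paragraph of Protocol 10.4, or put the restatement in the SAP:

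- Give an approximate one-sample figure, per antigen and per schedule, for the two-sided 95% interval to lie above no change: about 82% (t) with 90 subjects for a difference of 0.256, or 90% for a difference of about 0.287.
- Say that no formal test or success criterion is attached to it.
- Name the contrast (which post-third-dose sample against which earlier sample) and the scale to which 0.256 and 0.83 apply. If the intended contrast is with the post-second-dose sample, say so, because the SAP does not list that ratio.
- Separate drop-out from per-protocol exclusion. Either state that 90 is the expected PPS after all losses, or show the range (80%, 78% and 73% at a further 5%, 10% and 20%), labelled as an assumption.

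The cost is one rewritten paragraph with a less favourable figure. Enrolment, conduct and the planned analyses do not change.

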**CMI immunogenicity after third dose**

This second secondary objective aims to investigate on the cellular immunogenicity in a subset of 20 subjects per arm (40 subjects in total).

CMI will be evaluated as frequency of CD4+ T-cells expressing at least two different markers, when stimulated by each antigen PD, PE, P1A and UspA2.

**CONFIDENTIAL**207759 (NTHI MCAT-008)  
Protocol Amendment 3 Final

No inferential analysis is planned for CMI data and thus 40 subjects are considered to be sufficient for the purpose to report mean, median, min, max, Q1 and Q3 and represent them via boxplot.

**10.5. Cohorts for Analyses**

The following study cohorts will be evaluated.

**10.5.1. Exposed set**

The exposed set (ES) will include all subjects with at least 1 study vaccine administration documented, with respect to the vaccine actually administered:

- A **safety** analysis based on the ES will include all subjects with at least one vaccine dose administered and who provided safety data.

**10.5.2. Full Analysis Set**

The full analysis set (FAS) will include all subjects with at least 1 study vaccine administration for whom immunogenicity data are available:

- An **immunogenicity** analysis based on the FAS will include all vaccinated subjects for whom immunogenicity data are available.

The FAS analysis will be performed per treatment as planned in the randomization.

**10.5.3. Per-protocol set for analysis of immunogenicity**

**(Amended 26 May 2020)**

The per-protocol set (PPS) for immunogenicity will include all subjects in the FAS:

- Who met all eligibility criteria.
- For whom the administration of the vaccines was according to protocol.
- Who complied with the vaccination schedule, as specified in [Table 12](#) and [Table 6](#).
- Who received the study vaccines according to protocol procedures.
- Who did not receive a concomitant medication/ product leading to elimination from the PPS (per-protocol) analysis (see [Section 6.6.2](#)) up to the 1 month post-Dose 4 visit (Day 391).
- Who did not present an intercurrent medical condition leading to elimination from the PPS analysis for immunogenicity (see [Section 6.7](#)), up to the 1 month post-Dose 4 visit (Day 391).
- Who complied with the blood sample timings as specified in [Table 10](#) and [Table 6](#).
- For whom post-vaccination immunogenicity results are available for at least 1 assay.

**CONFIDENTIAL**207759 (NTHI MCAT-008)  
Protocol Amendment 3 Final

***Impact on the per protocol set for immunogenicity will be determined on a case by case basis.***

**10.6. Derived and transformed data****Demography**

- For a given subject and a given demographic variable, missing measurement will not be replaced.

**Safety**

- For solicited symptoms, missing or unevaluable measurements will not be replaced. Therefore the analysis of the solicited symptoms based on the ES will include only subjects/doses with documented safety data (i.e., symptom screen/sheet completed).
- For the unsolicited symptoms and concomitant medications/ products/ vaccinations, all vaccinated subjects will be considered and subjects who miss reporting symptoms/concomitant medications/ products/ vaccinations will be treated as subjects without unsolicited symptoms or concomitant medications/ products/ vaccinations, respectively.

**Immunogenicity**

- Calculation of the GMCs will be performed by taking the anti-logarithm in base 10 (anti-log10) of the mean of the log10 concentration transformations.
- Antibody concentrations below the assay cut-off will be given an arbitrary value of half the assay cut-off for the purpose of geometric mean concentration (GMC) calculation.
- A seronegative subject is defined as a subject whose antibody concentration is below the assay cut-off value (i.e. the ELISA lower limit of quantification).
- A seropositive subject is defined as a subject whose antibody concentration is greater than or equal to the assay cut-off value (i.e. the ELISA lower limit of quantification).
- For a given subject and the analysis of a given immunogenicity measurement, missing or unevaluable measurements will not be replaced.

**CMI**

- The frequency of CD4+ or CD8+ T-cells producing two or more markers (such as interleukin (IL)-2, IL-13, IL-17, interferon gamma (IFN- $\gamma$ ), tumour necrosis factor alpha (TNF- $\alpha$ ), upon *in vitro* stimulation with the antigen (induction condition) is calculated by adding an offset of 0.5 to the number of activated CD4+/CD8+ T cells (numerator) divided by the total number of CD4+/CD8+ T cells involved (denominator).
- The frequency of **antigen-specific** CD4+ or CD8+ T-cells for each individual subject is calculated as the difference between the frequency of CD4+ or CD8+ T-cells producing at least 2 cytokines/markers among IFN- $\gamma$ , IL-2, IL-13, IL-17, TNF- $\alpha$

**CONFIDENTIAL**207759 (NTHI MCAT-008)  
Protocol Amendment 3 Final

and/or CD40L, upon *in vitro* stimulation with the antigen (induction condition) minus the frequency of CD4+ or CD8+ T-cells producing at least 2 cytokines upon *in vitro* stimulation in medium only (background condition). For descriptive statistics purposes, differences less or equal to zero (0) are imputed to 1.

**10.7. Analysis of demographics**

Demographic characteristics such as age at enrolment, sex, race, ethnicity and smoking status will be summarised by study group using descriptive statistics:

- Frequency tables will be generated for categorical variable such as sex, race, ethnicity, age category, smoking status;
- Mean, median, standard deviation, minimum and maximum will be provided for continuous data such as age.

The distribution of subjects enrolled among the study sites will be tabulated as a whole and per study group.

Withdrawal status will be summarised by group using descriptive statistics:

- The numbers of withdrawn subjects will be tabulated according to the reason for withdrawal;
- The number of subjects enrolled into the study as well as the number of subjects excluded from PPS and FAS will be tabulated.

No inferential analyses of demographic data are planned.

**10.8. Analysis of safety**

The analysis for safety will be performed on the ES.

The number and percentage of subjects with at least one **local solicited AE**, with at least one **general solicited AE** and with any solicited AE during the 7-day follow-up period after each vaccination, will be tabulated with exact 95% confidence interval (CI), after each vaccination and overall by study group. The percentage of doses followed by at least one local solicited AE, by at least one general solicited AE and by any solicited AE will be tabulated overall by group with exact 95% CIs. The same computations will be done for Grade 3 solicited AEs.

The number and percentage of subjects reporting each individual solicited local and general AE during the 7-day follow-up period will be tabulated with exact 95% CI after each vaccination and overall by vaccine schedule. The percentage of doses followed by each individual solicited local and general AE will be tabulated overall by group with exact 95% CIs.

The same tabulation will be performed for Grade 3 AEs.

For fever, additional analyses will be performed by 0.5°C increments.

**CONFIDENTIAL**207759 (NTHI MCAT-008)  
Protocol Amendment 3 Final

All the unsolicited adverse events occurring within 30 days after each vaccination, judged either as probably related, possibly related, or not related to vaccination by the investigator, will be recorded.

The verbatim reports of **unsolicited** symptoms will be reviewed by a physician and the signs and symptoms will be coded according to the MedDRA Dictionary for Adverse Reaction Terminology. Every verbatim term will be matched with the appropriate preferred term (PT). The percentage of subjects with at least one unsolicited AE during the 30-day follow-up period after any study vaccination will be tabulated with its exact 95% CI for each group and by MedDRA PT. Similar tabulation will be done for the percentage of doses, for Grade 3 unsolicited symptoms.

The number of subjects who experienced any **pIMD** or any **SAE** from first vaccination up to 12 months post-Dose 4 will be reported.

The number of subjects who experienced any **SAE, death, pIMD or AE leading to study withdrawal**, from first vaccination up to study conclusion, and any **SAE related to study participation of concurrent GSK medication/ vaccination**, during the entire study period, will be reported.

In case of **Pregnancy** during the study, data follow-up and pregnancy outcomes will be described in detail.

The percentage of subjects using **concomitant medication/ product associated with an AE** will be summarised per group for each study vaccination and overall study vaccination.

